4.2 Exclusion Criteria

All candidates meeting any of the exclusion criteria listed below at baseline will be disqualified from study participation.

- Non-English speaking individual.
- Failure to provide informed consent;
- Allergy/sensitivity to grapes or Japanese knotweed;
- Current dietary supplementation of grape seed extract or ginko biloba;
- Consumption of ≥ 8 oz. of red wine/dealcoholized red wine/red or purple grape juice more than once weekly;
- Consumption of any dietary supplements containing resveratrol, quercetin, or *P. cuspidatum* in the previous 90 days;
- Active treatment for cancer, stroke (< 6 months), peripheral vascular disease, coronary artery disease, myocardial infarction (< 6 months), congestive heart failure (stage III or IV), valvular heart disease, major psychiatric disease, severe anemia (blood levels of Hemoglobin < 8 g/dl), bleeding disorders or other blood disorders, liver or renal disease, diabetes, severe osteoarthritis, blindness or deafness, fracture in upper or lower extremity (< 6 months), upper or lower extremity amputation, or Parkinson's disease;

- Cognitive impairment (i.e. Mini Mental Status Exam ≤ 23);
- History of significant head injury that currently interferes with functioning;
- Severe physical limitations (i.e., < 4 on the Short Physical Performance Battery);
- Hard exercise (i.e. running, bicycling, etc.) ≥ 30 min on five or more days per week;
- Excessive alcohol use (> 2 drinks/day) or alcohol abuse (> 5 drinks/day for males, or > 4 drinks/day for females);
- History of substance abuse within the past six months;
- Mood disorder (i.e. Center for Epidemiological Studies Depression (CES-D) ≥ 16);
- History of tobacco use within the past three years;
- Resting heart rate > 120 bpm at screening visit;
- Systolic blood pressure > 160 mm Hg at screening visit;
- Diastolic blood pressure > 90 mm Hg at screening visit;
- Fasting glucose ≥ 126 mg/dL at screening visit;
- Abnormalities in blood chemistry parameters, defined by blood chemistry marker outside of healthy range) as determined by study physician;
- Current use of
 - o anabolic treatments (e.g. growth hormone or testosterone),
 - o anticholinesterase inhibitor (e.g. Aricept),
 - o hormone replacement (e.g. Estrogen),
 - o anticoagulant therapies (note: aspirin -anti-platelet use (≤ 81 mg/day) is permitted) or
 - o use of anti-inflammatory medications more than 3 times per week

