5.3.3 Prohibited Interventions

- Active treatment for cancer, stroke, peripheral vascular disease, coronary artery disease, myocardial infarction, congestive heart failure (stage III or IV), valvular heart disease, major psychiatric disease, severe anemia, liver or renal disease, diabetes, severe osteoarthritis, blindness or deafness, fracture in upper or lower extremity, upper or lower extremity amputation, or Parkinson's disease;
- Physical activity (i.e., running, bicycling, etc.) ≥ 120 min/week;
- Use of anabolic medications (e.g. growth hormones or testosterone), anticholinesterase inhibitor (e.g. Aricept), or anticoagulant therapies (aspirin use is permitted);
- Dietary supplementation of grape seed extract or ginko biloba;
- Consumption of any dietary supplements containing resveratrol, quercetin, or *P. cuspidatum*;
- Use of other Investigational products;
- Dietary supplementation with CoQ10 or alpha-lipoic acid.

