Risks associated with resveratrol supplementation: Toxicity from the doses of resveratrol used in this study is likely to be low based on animal studies, and doses of 1000 mg/day have been well tolerated in previous safety trials in young and middle-age adults.[58-60] Additionally, a recent repeated-dosing study found that a dose of 200 mg of resveratrol at eight hour intervals for a three day period was well tolerated in older adults (age $\geq 65 \text{ years}$),[61] and doses of 1000 mg/day, 1500 mg/day, and 2000 mg/day of resveratrol supplementation were well tolerated in older adults during a four week intervention.[56] Based on the findings described above, we have chosen the test doses of resveratrol chosen for the proposed study to be 1000 mg/day and 1500 mg/day. Adverse effects of resveratrol have not been reported at these doses; however, long-term side effects are not known. Resveratrol is structurally similar to the synthetic estrogen diethylstilbestrol, and may have estrogenic activity. Resveratrol might also interact with blood thinners such as warfarin, and non-steroidal anti-inflammatory medications, thereby increasing the risk for bleeding. In our resveratrol pilot study, *The RIPE Trial*, resveratrol supplementation at 1000 mg/day had minimal effects on blood chemistries, and there were no significant differences in the number of participants reporting adverse or toxic events (e.g. headaches) across the three conditions (all p values > 0.05).

Risk management in participants using prohibited medication/interventions after study enrollment.

If the participant reports any change in medications, this information will be recorded in the participant's file (i.e., source documents and case report forms). If a participant reports use of any prohibited interventions as listed below and in sections 5.3.3. of the protocol (Prohibited Interventions) post-randomization, the participant will be withdrawn from the study.

Prohibited Interventions

• Active treatment for cancer, stroke, peripheral vascular disease, coronary artery disease, myocardial infarction, congestive heart failure (stage III or IV), valvular

heart disease, major psychiatric disease, severe anemia, liver or renal disease, diabetes, severe osteoarthritis, blindness or deafness, fracture in upper or lower extremity, upper or lower extremity amputation, or Parkinson's disease; - Safety Reasons

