- Hard Exercise (i.e., running, bicycling, etc.) ≥ 30 min/day on 5 or more days per week; *Scientific Reasons*
- Use of anabolic medications (e.g. growth hormones or testosterone), anticholinesterase inhibitor (e.g. Aricept), or anticoagulant therapies (aspirin use > 81 mg/day; aspirin use < 81 mg/day is permitted); -Safety Reasons
- Dietary supplementation of grape seed extract or ginko biloba; Scientific Reasons
- Consumption of any dietary supplements containing resveratrol, quercetin, or *P. cuspidatum; Scientific Reasons*
- Use of other Investigational products; Safety and Scientific Reasons
- Dietary supplementation with CoQ10 or alpha-lipoic acid. Scientific Reasons

If the participant reports changes in health, medications, or lifestyle other than the interventions listed above, the study physician will evaluate the safety of participants to continue in the intervention based on these reported changes. In these circumstances, the role of the study physician will be to provide recommendations to the study team regarding whether or not the participant should continue in the study based on reported changes in health, medication use, or lifestyle.

Adverse events will be graded according to Common Terminology Criteria for Adverse Events (CTCAE) v 4.03. In compliance with the Federal Registry, 21 CFR 312.32, effective April 1, 2008, we will use the following definitions for adverse event reporting:

Adverse event means any untoward medical occurrence associated with the use of a drug in humans, whether or not considered drug related.

Life-threatening adverse event or life-threatening suspected adverse reaction. An adverse event or suspected adverse reaction is considered "life-threatening" if, in the view of either the investigator or sponsor, its occurrence places the patient or subject at immediate risk of death. It does not include an adverse event or suspected adverse reaction that, had it occurred in a more severe form, might have caused death.

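### Section 7.1 requires withdrawal from the study for any listed prohibited intervention, Sections 4.3 and 9.4 treat such cases differently, and the exercise trigger has two limits

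*Combined protocol and SAP*

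**What the plan says.** Section 7.1 (risk management after enrolment) is mandatory. If a participant reports a prohibited intervention "post-randomization, the participant will be withdrawn from the study". The trigger covers interventions "as listed below and in sections 5.3.3. of the protocol (Prohibited Interventions", so both lists apply. The 7.1 list gives a reason for each of its seven items. Three carry a safety reason, one of these (other investigational products) together with a scientific one. Four carry a scientific reason only: hard exercise; grape seed or ginkgo, "Dietary supplementation of grape seed extract or ginko biloba; Scientific Reasons"; supplements containing resveratrol, quercetin or P. cuspidatum; and "Dietary supplementation with CoQ10 or alpha-lipoic acid. Scientific Reasons". Physician review is reserved for other events, namely a new health state, a new drug or a change of "lifestyle other than the interventions listed above, the study physician will evaluate the safety of participants to continue in the intervention".

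Section 4.3, on managing prohibited medication or interventions after enrolment, has the use recorded and leaves continuation in the study to the investigator and study physician. Section 9.4 allows product to be stopped, temporarily or permanently, with the participant still on study. Its reasons include non-compliance and medication use.

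Exercise appears three times. Section 5.3.3 bars "Physical activity (i.e., running, bicycling, etc.) ≥ 120 min/week". Section 7.1 bars "Hard Exercise (i.e., running, bicycling, etc.) ≥ 30 min/day on 5 or more days per week". The entry exclusion in 4.2 is "Hard exercise (i.e. running, bicycling, etc.) ≥ 30 min on five or more days per week".

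**The concern.** Staff have two incompatible instructions for one event. Under 4.3 a participant who starts CoQ10 is discussed and may continue; under 7.1 the same participant must leave. For exercise there are also two limits, both invoked by the same withdrawal sentence.

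What is at stake is follow-up data. Section 9.3 defines the intent-to-treat set for the primary outcome as participants with both biopsies. If 7.1 is followed literally and the second biopsy is not obtained, a participant leaves the primary analysis because of something done after randomisation. For the four items barred on scientific grounds alone, no participant-safety reason is given for ending follow-up. The scientific concern is already handled by the per-protocol set, which excludes users of prohibited therapies.

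**Working it through.** **1. The instructions side by side.**

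| Section | Event | Instruction |
|---|---|---|
| 7.1 | Any item listed in 7.1 or 5.3.3 | Withdrawn from the study, no discretion |
| 4.3 | Prohibited medication or intervention | Investigator and study physician decide |
| 9.4 | Includes non-compliance and medication use | Product may be stopped, participant remains on study |
| 8 | Includes non-compliance and medication use | May be removed; followed, with permission, if product is discontinued |
| 9.2 | Withdrawals | Try for a second biopsy on every participant |
| 9.3 | Prohibited therapy | Out of per protocol; intent-to-treat needs both biopsies |

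The conflict of 4.3 with 7.1 is direct. Section 4.3 names prohibited interventions, so it cannot be confined to unlisted changes. Section 9.4 is in tension with 7.1, though it is permissive. Sections 8, 9.2 and 9.3 do not strictly contradict 7.1, but they show an intent to keep following participants and to obtain the second biopsy.

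**2. Exercise limits.** The least that breaches 7.1 or the entry criterion is 5 x 30 = 150 min/week. Section 5.3.3 is breached at 120 min/week. Cycling 4 x 30 = 120 min/week passes 4.2 and the 7.1 list but breaches 5.3.3. So does 4 x 60 = 240 min/week. Because the 7.1 sentence invokes 5.3.3, both people must be withdrawn for a habit that entry allowed.

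**3. What lost biopsies would cost.** Section 9.2 states 80% power at 0.69 SD with 18 completers per arm and correlation 0.7. With those inputs:
- SD of change = sqrt(2 x (1 - 0.7)) = 0.775 baseline SD.
- Contrast SE = 0.775 x sqrt(1.5/18) = 0.224.
- Noncentrality = 0.69/0.224 = 3.09; Satterthwaite df = 34.
- Power = 85.0%, so the stated 80% is not reproduced; it is on the conservative side. That is a separate matter.

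The plan allows for 20 - 18 = 2 losses per arm. If more were lost, equally across arms (an assumption), power at 0.69 SD would be:

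| Biopsied per arm | Plan inputs | SD set to give 80% at 18 |
|---|---|---|
| 18 | 85.0% | 80.0% |
| 16 | 80.4% | 74.9% |
| 14 | 74.5% | 68.7% |

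**4. Selective loss through exercise (all inputs assumed).** Let reported exercise and monitored activity be standard normal with correlation 0.5. Treatment shifts activity by d and reported exercise by s, where s = 0.5d (scaled) or s = d (unscaled). A participant is lost above the cut-off c = z(1 - p), where p is the placebo breach rate. With G(x) = phi(x)/Phi(x), attenuation = 0.5 x [G(c - s) - G(c)]/d, and the share lost per active arm = 1 - Phi(c - s).
- Rare breaches (p 0.5% to 2%, d 0.3 to 0.5): attenuation 1.1% to 3.2% scaled, 2.6% to 7.8% unscaled; 0.15 to 0.71, or 0.23 to 1.20, of 20 lost per active arm.
- Extreme (p 15%, d 0.7): attenuation 10.3% scaled, 23.0% unscaled; but then 1 - Phi(1.036 - 0.35) = 24.6%, or 4.9 of 20, and 1 - Phi(1.036 - 0.70) = 36.8%, or 7.4 of 20, are withdrawn per active arm, against 3 of 20 on placebo.
- State 3, assumed correlation with reported exercise 0.1 to 0.3: shift = r x [G(c - s) - G(c)] x 0.775, at most 0.033 (scaled) or 0.075 (unscaled) baseline SD. At SD 40 that is 1.3 or 3.0 units, against 0.69 x 40 = 27.6 units.

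These figures assume that nobody is brought back and that every breach is reported before the 90-day tests.

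**The case against.** A reader might infer that the whole follow-up plan contradicts 7.1. It does not. Section 8 itself permits removal for non-compliance or medication use, and its follow-up sentence depends on permission. Section 9.2 deals with withdrawals, so a participant withdrawn under 7.1 could still be asked for the biopsy. Section 9.3 is compatible too: someone whose use is reported late, or whose biopsy is recovered, is in the intent-to-treat set and out of per protocol. Withdrawn could also be read as off product, although 7.1 does not say so and 9.4 distinguishes stopping treatment from leaving the study.

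A reader might also infer that the rule removes responders and materially biases the activity comparison, since the exploratory hypotheses expect more spontaneous activity. The documents do not support that. The outcome is monitored activity; the trigger is reported running, cycling or similar. Nothing in the documents says that resveratrol would lead people aged 65 or over to take up hard exercise, and no mechanism is given for differential loss through the supplements. The 30- and 60-day visits list no exercise question, so reports would come mainly by diary. A breach first reported at 90-Day Visit 1 arises when the walk, SPPB and Biodex tests are being done. The upper attenuation figures require implausible withdrawal numbers, a pattern that the withdrawal-rate comparison in 9.2 is meant to examine.

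Both replies stand. Neither removes the direct conflict of 4.3 with 7.1 or the two exercise limits.

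**Conclusion.** The point holds as a contradiction in current text, and it is minor. The mandatory rule in 7.1 conflicts with the discretion in 4.3 and sits badly with 9.4. The two exercise limits require withdrawal of some people whom entry admits. These findings rest on wording and simple arithmetic, and confidence in them is high.

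The size of any data loss cannot be fixed, because the documents give no rate of prohibited use. If breaches are rare, the losses fall within the allowance of two per arm and the effect on State 3 is likely negligible. Selective loss on the exploratory activity outcome is possible but speculative, and the attenuation figures illustrate assumed inputs only.

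**What to change.** Make Sections 4.3 and 7.1 agree for every listed item:
- **Safety-labelled items**, including other investigational products: study product is stopped. This changes the present rule, which is withdrawal from the study.
- **Items labelled for scientific reasons only:** use is recorded, and the investigator and study physician decide whether product continues.
- **All items:** with permission, the participant stays in follow-up, including the 90-day tests and, unless medically contraindicated (for example by anticoagulant use), the second biopsy. Analysis is by intent-to-treat as 9.3 defines it, so anyone without a second biopsy still falls outside the primary set. The per-protocol set continues to exclude users of prohibited therapies.

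In 5.3.3, use the exercise limit already in 4.2 and 7.1. This is the looser limit and would allow 4 x 60 = 240 min/week, but it is the one under which participants enrol.

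The cost is amendment wording, since the 90-day tests and biopsy are already scheduled. The downside is slight added noise or dilution in State 3 from exercise or supplement use. The documents do not quantify it, and the per-protocol analysis offers a check for prohibited therapies.

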7.2 Methods and Timing for Assessing, Recording, and Analyzing Safety Parameters

As noted above, we will monitor potential adverse events associated with resveratrol consumption by blood work analysis (complete metabolic panel and complete blood count) and National Cancer Institute (NCI) criteria during all study visits, **baseline**, **day 30**, **day 60**, **day 90**, as well as at both10-day Post-Biopsy and 30 day follow-up visits (see **Table 1**). All assessment visits will be conducted at a central location, and all sessions will be conducted and supervised by a trained research staff, who will monitor potential adverse experiences and symptoms.

7.3 Adverse Events and Serious Adverse Events

Adverse Event – An adverse event (AE) is defined as any untoward medical occurrence associated with the use of a drug in humans, whether or not considered drug related. An adverse event (also referred to as an adverse experience) can also be any unfavorable and unintended sign (e.g., an abnormal laboratory finding), symptom, or disease temporally associated with the use of a drug, without any judgment about causality. An adverse event can arise from any use of a drug (e.g., off label use, use in combination with another drug) and from any route of administration, formulation or dose, including overdose.

Serious Adverse Event (SAE) - Any AE that results in one or more of the following outcomes:

- Death
- A life-threatening event
- Inpatient hospitalization or prolongation of existing hospitalization
- A persistent or significant disability/incapacity
- A congenital anomaly or birth defect
- An important medical event based upon appropriate medical judgment

Serious adverse events (SAEs) that are unanticipated and/or possibly related to study participation are reported to the NIH within 48 hours of learning of the event, to the IRB and Independent Safety Board (oversight committee) within five business days of learning of the event. If an event, incident, experience, or outcome is life-threatening or fatal, the IRB must be notified by phone within 24 hours.

Any unexpected fatal or life-threatening suspected adverse reactions will be reported to the FDA no later than 7 calendar days after the initial receipt of the information. For SAEs that are not fatal or life-threatening, the time frame for submitting an IND safety report to FDA is no later than 15 calendar days after the investigator-sponsor determines that the suspected adverse reaction or other information qualifies for reporting.

Minor events will be reported to the University of Florida's Health Science Center IRB at the time of annual review, as well as to the oversight committee on a bi-annual basis. Both the principal investigator and the study staff will review the study weekly and examine reports of adverse incidents and reports of study participant recruitment and follow-up. Throughout the course of the study, information regarding issues deemed critical to the study or to the safety of research participants will be provided to the principal investigator and primary mentors. As a result of

receiving this critical information, a meeting to discuss this critical information may be convened. Information deemed critical would include:

- serious and non-serious adverse events that may occur,
- suspicion of scientific fraud or misconduct,
- any other issues which may warrant protocol changes or modifications.

Monitoring of both AEs and SAEs will be achieved via administration of structured questionnaires. Standardized forms for referring and treating study participants who experience adverse events will be in place.

 Classification of AE Severity – Adverse events will be graded according to Common Terminology Criteria for Adverse Events (CTCAE) v 4.03. The study physician will be responsible for all trial-related medical decisions and the review of AEs throughout the study. The physician will assess AEs and will ensure that they are recorded in detail. Adverse events, whether in response to a query, observed by study team, or reported spontaneously, will be reported on the appropriate CRF and/or source document.

AE Attribution Scale – All adverse events (AEs) will also be categorized according to the likelihood that they are related to the study intervention. Specifically, they will be labeled either definitely, probably, possibly, or unrelated to the study intervention. The classification of potential relationship to the intervention is shown in **Table 2**.

Table 2. Adverse Event (AE) Classification

Adverse Event (AE) Classification		
Definite.	Temporal pattern + known or expected AE response pattern + confirmed by	
	stopping the intervention + reappearance of AE on re-challenge	
Probable.	Temporal pattern + known or expected AE response pattern + confirmed by	
	stopping the intervention + could not be explained by participant's clinical state	
Possible.	Temporal pattern + known or expected AE response pattern + could have been	
	produced by a number of other factors	
Unknown.	Relationship for which no evaluation can be made	
Not related.	AE for which sufficient information exists to indicate that the cause is unrelated	
	to the study intervention	

As noted above, we will also monitor potential adverse events associated with resveratrol consumption by blood work analysis (complete metabolic panel and complete blood count) and National Cancer Institute (NCI) criteria during all study visits: baseline, day 30, day 60, day 90, as well as at the both10-day Post-Biopsy and 30 day follow-up visits (; see **Table 1**). If a blood marker falls in the abnormal range, the study physician will be consulted and will determine whether it is safe for the participant to continue in the trial.

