8. INTERVENTION DISCONTINUATION

Participants may be removed from the study for the following reasons: (1) Unacceptable toxicity (≥ grade 2 toxicity) related to administration of resveratrol using the NCI toxicity criteria; (2) participant voluntarily decides to withdraw; (3) participant non-compliance with the study protocol; or (4) intercurrent disease, medication use, or condition that would affect the assessment of the participant's status. With their permission, participants will continue to be followed if study intervention is discontinued. This study will be stopped prior to its completion if: (1) the intervention is associated with adverse effects that significantly impact the risk-benefit ratio, (2) study recruitment or retention becomes futile, (3) any new information becomes available during the trial that necessitates stopping the trial; or (4) if the oversight committee indicates that discontinuation of the trial is necessary due to adverse event frequency or severity.

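### Table 2 makes a known or expected response pattern a condition of every related label, so a novel but plausible reaction to resveratrol has no related category, contrary to the protocol's own causality definition

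*Combined protocol and SAP*

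**What the plan says.** Section 7.3 of the combined protocol and SAP applies one attribution scale to all adverse events. The introductory sentence gives four labels: "Specifically, they will be labeled either definitely, probably, possibly, or unrelated to the study intervention". Table 2, to which it then points, has five rows.

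- **Definite** and **Probable** both open with "Temporal pattern + known or expected AE response pattern + confirmed by" stopping the intervention, and each adds one further condition.
- **Possible** is "Temporal pattern + known or expected AE response pattern + could have been" produced by several other factors.
- **Unknown** is "Relationship for which no evaluation can be made".
- **Not related** is "AE for which sufficient information exists to indicate that the cause is unrelated" to the intervention.

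On what is already known of harm, Section 7.1 states: "Adverse effects of resveratrol have not been reported at these doses; however, long-term side effects are not known".

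Two clauses elsewhere use relatedness. Section 8 allows removal for toxicity "related to administration of resveratrol using the NCI toxicity criteria". Section 9.4 allows treatment to be discontinued for toxicity related to resveratrol, and refers to Table 4.

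**The concern.** A causality scale should ask whether the product may have caused the event. Whether the event was already known is a separate question, and Table 2 folds it into the first. With few established adverse effects at the study doses, a new reaction is what the safety monitoring most needs to recognise, and Section 9.4 states the purpose of determining the short- and long-term toxicities of two doses. If staff apply the table as worded, a novel reaction receives a label that does not mark it as possibly caused by resveratrol. Any rule that takes relatedness from that label will then miss it.

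**Working it through.** No sample size, error rate or event count bears on this point, so there is no figure to reproduce. The check is logical: take one type of event through Table 2, then compare the result with the protocol's other rules.

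**Step 1. Test event.** An adverse event starts at a plausible time after dosing. Its pattern is not known or expected for resveratrol. Nothing shows another cause. The criteria in each related row are joined by plus signs, so all must be met.

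| Row | Condition that decides it | Result |
|---|---|---|
| Definite | known or expected pattern | fails |
| Probable | known or expected pattern | fails |
| Possible | known or expected pattern | fails |
| Not related | positive information that the cause lies elsewhere | fails |
| Unknown | no evaluation can be made | fits only if the assessor regards a plausible time link as not assessable |

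None of the 3 related rows is available. The only candidate row is Unknown, and it is absent from the four-label sentence.

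**Step 2. Compare with the rest of the protocol.**

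- Section 7.1 defines a suspected adverse reaction by a reasonable possibility that the drug caused it. Expectedness is not part of the definition.
- Section 7.1 separately defines an unexpected suspected adverse reaction. An event can therefore be both unexpected and suspected to be drug-related.
- Section 7.1 lists expectedness and relationship as separate items in the weekly evaluation.
- Section 7.3 requires unexpected fatal or life-threatening suspected reactions to reach the FDA within 7 calendar days.

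Table 2, read literally, leaves empty the class (unexpected and related) that Section 7.1 defines and Section 7.3 requires to be reported. No passage overrides the table or adds a category for a new reaction.

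**Step 3. Trace where the label is used.**

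| Element of the plan | Depends on a related label? |
|---|---|
| Subjects with grade 1–5 events (9.4, item A) and change in blood chemistries (item B) | No |
| Off-cycle board review for one grade IV or two grade III toxicities (9.4) | No |
| Table 4 temporary stops | No; identical in all arms, including placebo |
| Unanticipated serious events to the NIH and IRB (7.3, 7.4, 7.6) | No |
| Serious events to the safety board under 7.3 and 7.4 | No, if unanticipated |
| Serious events to the safety board under 7.6 | Yes; that route names possibly related events, and lists unanticipated ones for the NIH and IRB only |
| Attribution label of each event (7.3) | Yes |
| Toxicity clauses in 8 and 9.4 | Yes, if relatedness is taken from Table 2 |

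**The case against.** The strongest reply is that little of the safety system runs on this label. That is largely right, as the last table shows. The oversight committee can also stop the trial for the frequency or severity of adverse events whatever their attribution. The study physician reviews any abnormal blood marker. Sections 8 and 9.4 each allow removal or discontinuation for an intercurrent disease or condition without a relatedness test. Neither toxicity clause cites Table 2, and both are permissive. FDA reporting can follow the definition in Section 7.1 if staff use that rather than the table.

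Three stronger readings are tempting, and the documents do not support them.

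- *A novel event is forced into Not related.* A reader might infer this from the four-label sentence. But Not related requires positive information about another cause, and the table to which the text points supplies Unknown.
- *The related-event rate is driven to zero in the results.* No table or rate of related events is planned. The toxicity description in Section 9.4 counts all graded events. The Fisher's exact test in Section 9.2 is on the occurrence of side effects, which is not defined through Table 2.
- *No response pattern is known, so nothing could ever be called related.* Section 7.1 names possible estrogenic activity and bleeding through interaction with blood thinners or non-steroidal anti-inflammatory drugs, and gives headache as an example from the pilot study. The known set is small, not empty.

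These points limit the consequence. They do not repair the scale, which is the only one in the documents and covers every adverse event.

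**Conclusion.** The concern holds in a limited form. Table 2 is a stated rule that conflicts with the protocol's own definition of a suspected adverse reaction, so this is more than missing detail. Its size is qualitative: for a temporally plausible reaction with a new pattern, 0 of 3 related labels can be assigned. The practical exposure is the attribution of non-serious events, the causality label that would support calling an event a suspected adverse reaction, and the narrower safety-board route in Section 7.6. The toxicity clauses in Sections 8 and 9.4 join that list only if their relatedness is read from Table 2, which is an inference because neither says so.

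The conclusion assumes that assessors apply Table 2 as written. If they already follow the reasonable-possibility definition in practice, the labels may be sound and only the text is wrong. No efficacy analysis or all-cause safety comparison between arms is affected.

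**What to change.** 1. Remove the known-or-expected-pattern condition from Possible, so that it rests on a plausible time relationship with other explanations also open, in line with the reasonable-possibility definition in Section 7.1. The stronger labels can keep the pattern condition, because a novel reaction would then have at least one related category.
2. Keep expectedness as the separate weekly assessment that Section 7.1 already lists.
3. Make the sentence above Table 2 and the table agree on the number and names of the labels, including whether Unknown is a permitted label.
4. Reconcile Section 7.6 with Sections 7.3 and 7.4 on which serious events go to the safety board. State in Sections 8 and 9.4 whether their use of relatedness means the revised scale. What the discontinuation rule itself should be is for the investigators, and none is proposed here.

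The cost is a wording change to the protocol and the case report form. Somewhat more events will be labelled possibly related. Because the study staff in contact with participants are blinded (Section 6.2.3), that should be expected in all arms, including placebo.
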